### Aim 3 Hypothesis Testing Plan

***Hypothesis 5:*** *Those with greater SDA will demonstrate reduced event-related potential component amplitudes differences between negative vs. positive feedback about per-trial progress toward a reward.* We will employ a linear mixed model to test if SDA predicts positive and negative feedback-related N200 and P300 amplitude differences at baseline. Age, gender, biological family history of alcoholism density, and race will be used as covariates. We will explore a secondary linear mixed model analysis (co-varying for BrAC) using the ERP component differences between baseline and at **1**) maximum BrAC and **2**) terminal work for alcohol.

***Hypothesis 6a:*** *Those with greater SDA will demonstrate greater resting state crosstalk (less differentiation) between the default mode and fronto-parietal networks.* Our preliminary results (Figure 5, above) suggest that advancing AUD severity increases communication between networks that are functionally independent (i.e., the default mode network is prominent at rest, while the fronto-parietal network is activated by focused mental activity). As we hypothesize that SDA marks increasing AUD severity, we similarly hypothesize that SDA is related to abnormally increased communication between the default mode and fronto-parietal networks. To test this hypothesis, whole-brain functional connectivity (FC) will be estimated for each individual participant using a data-driven, functionally based parcellation and characterized for segregation/modularity, which reflects the underlying organization into functional modules or communities. Age will be a covariate in all analyses. Furthermore, to characterize the tendency of brain regions to belong to the same module as a fine-grain continuum (as opposed to an integral membership), we use the consensus clustering approach. The pairwise correlations between module consensus and SDA of participants represent a mapping of SDA into the functional connectome domain. To control for false positives, the correlation between segregation/modularity (consensus clustering approach) and SDA will be z-normalized using 10,000 permutation tests, where the SDA vectors will be randomly shuffled and their associations with modularity consensus mapped 10,000 times, producing a distribution of expected SDA associations by chance. Based on the mean and standard deviation of this null distribution, the actual SDA associations can be z-scored and thresholded at  $p < 0.05$  (equivalent to a two tailed, i.e.,  $|z| > 1.96$ , for significant associations). To minimize false positives, we will also incorporate the equivalent of an extent threshold for network-based associations to account for the effect size (as measured by number of edges in connected components or by their spatial pairwise clustering) of the associations in the functional connectome domain. We will also consider using the Permutation Network Framework (PNF), which makes no assumptions about the distribution of the test statistics, since they often show non-standard distributions due to the intrinsic complex nature of brain connectivity data. To evaluate the robustness and reproducibility of these results, other gray matter parcellation schemes will also be assessed, using atlases that range from coarser to finer resolutions (from anatomically-based with 84 regions to multimodal with 360 regions, respectively). Using a similar approach, we will evaluate the associations between SDA and the network properties of integration and centrality. Integration reflects communication efficiency, often reflected by distance to closure

transformations of the shortest-path-lengths between nodes. Centrality measurements rank the relevant brain regions based on how central the nodes are and cover communicability aspects such as degree (number of edges per region) or the number of shortest-paths through each region (betweenness centrality).

**Hypothesis 6b:** *Those with greater SDA will demonstrate reduced ventral striatal-ventromedial frontal connectivity.* We will complement the connectome approach by using a seed-based approach to test voxel-level functional connectivity between the ventral striatum and ventromedial prefrontal cortex and its relation to SDA. For each subject, the functional connectivity between the ventral striatal seed (Figure 7d, red seed region) and all other cerebral gray matter voxels will be computed and transformed to MNI standard space for each subject. Age will be a covariate in all analyses. Finally, the resulting ventral striatal seed-to-gray-matter voxel-level FC estimations will be correlated (Pearson's coefficient) with subjects' SDA, yielding a high resolution (voxel-level) mapping of SDA onto fronto-striatal connectivity patterns. To control false positive findings, a multiple comparison correction based on false discovery rate will be applied ( $p_{FDR} < 0.05$ ) with an extent threshold ( $k=50$ ) to avoid spurious isolated voxels and small clusters.

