*Hypothesis 4:* Significant factors from hypothesis 3 will identify a latent trait that classifies individuals into two types: those who have high SDA and those who have low SDA.

Aim 3: Identify signatures of neural function that underlie SDA.

*Hypothesis 5:* Those with greater SDA will demonstrate reduced event-related potential component amplitudes differences between negative vs. positive feedback about per-trial progress toward a reward. Those with greater SDA will demonstrate

*Hypothesis 6a:* greater resting state crosstalk between the default mode and fronto-parietal networks and *Hypothesis 6b:* reduced ventral striatal-ventromedial frontal connectivity.

The positive impact of this project will be to advance the translation between preclinical and clinical models and to elucidate distinct mechanisms underlying AUD progression in humans. Importantly, the proposed model uses objective behavior, rather than subjective symptom report. Our human component project is centered on the IARC theme and complements its preclinical components and methodologies. We expect that the results will facilitate the identification and evaluation of pharmacologic and behavioral interventions to minimize the risk of AUD progression risk in drinkers who have yet to manifest treatment resistant behavior.

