**Figure 4. Schedule of Work.** The amount of work required per reward increases geometrically. At most, 14 work-sets of a single type can be completed in the 2.5-hour voluntary self-administration interval. Thus, cumulative work will range up to 850 correct and 850 incorrect SDA trials performed. BrAC sampling or collection of subjective perceptions is performed during the 2.5 min required for reward delivery.

During a work set (below), the left-most symbol in the sequence is presented on the subject's monitor until the subject initiates a trial by pressing and holding down a 2-in diameter button (labeled here with the reward type "A" for alcohol, or "W" for the alternative reinforcer, water).

The press-and-hold causes an immediate display change: the outer ring of the symbol immediately turns from white to yellow signifying the onset of an anticipatory interval of unpredictable duration. Simultaneous with the change in outer ring color, an image will occupy the display, hiding the other visual stimuli (substituted for the reward indication for demonstration purposes). The subject may also be presented with a sound during this uncertainty interval. The nature of this image and sound will vary by session and reward – neutral for water and either neutral or aversive for alcohol dependent upon the session and selected from the International Affective Picture Scale, similar to our prior protocols (IRB # 1505788344). During this interval, the subject prepares to release the button as soon as the brief response window opens, indicated by color change of a random area of the image to blue. To count as a success, the subject must release the button within the response window; i.e. before the blue area disappears. Button release will terminate the display of the image. The SDA work task is adaptive: with success (green), the trial is counted towards the work-set requirement and the response window for the next trial is shortened; with failure (red), the response window lengthens; thus the overall success rate is specified independent of the effects of alcohol or fatigue.

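### Hypothesis 6a: z-scoring with the mean and SD of the shuffled null is just a fixed cut on |r|; the null's shape is ignored and the two error tails can be unbalanced

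*Combined protocol and SAP*

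**What the plan says.** The edge-level test is in the combined protocol and SAP, section 7.0, Aim 3 Hypothesis Testing Plan, Hypothesis 6a.

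- **Statistic.** "The pairwise correlations between module consensus and SDA of participants represent a mapping of SDA into the functional connectome domain". The type of correlation is not named here; Pearson is named only for Hypothesis 6b.
- **Null.** A permutation scheme, "where the SDA vectors will be randomly shuffled and their associations with modularity consensus mapped 10,000 times".
- **Decision.** "Based on the mean and standard deviation of this null distribution, the actual SDA associations can be z-scored and thresholded at" p < 0.05, which the plan equates with a two-tailed |z| > 1.96.
- **Other safeguards.** An extent threshold will be added, with no size or calibration stated. The Permutation Network Framework (PNF) will be considered, as a method that "makes no assumptions about the distribution of the test statistics, since they often show non-standard distributions". Power Analyses repeats the choice: permutation plus extent threshold, or PNF instead.

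The hypothesis has a direction: "Those with greater SDA will demonstrate greater resting state crosstalk (less differentiation) between the default mode and fronto-parietal networks". SDA is defined under Hypothesis 1 as the cumulative trials worked for alcohol in the aversive session. The Figure 4 legend in section 5.0 says "The amount of work required per reward increases geometrically", with at most 14 work-sets of one type and 850 correct trials. The distributions of SDA and of module consensus are not given. Section 4.0 says that a subset is scanned, without a number; Power Analyses argues from n = 100 and a pilot of 51.

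**The concern.** A permutation null is worth computing because it shows the shape of the null distribution, above all its tails. The plan reduces that null to two moments and then applies a normal cut-off. For a correlation, both moments are known before any shuffling. The plan also says that statistics of this kind often do not follow standard distributions, and that is when 1.96 is least secure.

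Two things are at stake. First, a reader of the results would take the edge map to rest on a permutation-based threshold, when at the edge level it rests on a parametric one. Second, H6a predicts a positive association, so the upper tail matters most, and a skewed null would leave that tail with an error rate other than 2.5%. The plan extends a similar approach to integration and centrality, so the same rule would carry over to those analyses.

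**Working it through.** **1. The plan's own figure.** 2 × [1 − Φ(1.96)] = 0.0500. It reproduces, provided that the null is normal.

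**2. Moments of the shuffled null.** Standardise SDA (x) and consensus (y) so that each sums to 0 and each sum of squares is n. Then r = (1/n) Σ x_π(i) y_i. Over random permutations each x_π(i) has mean 0 and variance 1, and any two have covariance −1/(n−1). So E(r) = 0 and

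Var(r) = (1/n²)[n + n/(n−1)] = 1/(n−1).

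Hence z = r√(n−1) for any data. With 10,000 shuffles on several data shapes, the largest absolute mean was 0.0017. The SDs were 0.0996–0.1007 against 0.1005 at n = 100, and 0.1413–0.1422 against 0.1414 at n = 51.

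**3. The rule in terms of r.**
- n = 100: 1.96/√99 = 0.197 (t-test cut 0.1966)
- n = 51: 1.96/√50 = 0.277 (t-test cut 0.276)

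**4. Error per tail when there is no association.** The shapes are assumed, since the documents give none. There were 200,000 simulated data sets per row, using Pearson r. Low consensus is Beta(0.5, 4.5), mean 0.10; high consensus is Beta(4.5, 0.5), mean 0.90. Entries are % upper / lower / total.

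| SDA; consensus | n = 100 | n = 51 |
|---|---|---|
| normal; normal | 2.55 / 2.44 / 4.98 | 2.49 / 2.51 / 4.99 |
| exponential; normal | 2.50 / 2.52 / 5.02 | 2.38 / 2.52 / 4.89 |
| uniform; low | 2.46 / 2.48 / 4.94 | 2.40 / 2.43 / 4.82 |
| both gamma, skew 1 | 2.71 / 2.19 / 4.90 | 2.76 / 2.09 / 4.85 |
| both exponential | 3.31 / 1.49 / 4.80 | 3.51 / 1.23 / 4.74 |
| exponential; low | 3.38 / 1.44 / 4.82 | 3.58 / 1.13 / 4.71 |
| lognormal; low | 3.96 / 0.85 / 4.80 | 4.20 / 0.61 / 4.81 |
| exponential; high | 1.46 / 3.38 / 4.84 | 1.15 / 3.65 / 4.80 |
| left-skewed; low | 1.46 / 3.33 / 4.79 | 1.12 / 3.61 / 4.73 |

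The total stays at 4.7–5.0%. Only the split between tails moves, and its direction follows the two skews.

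**5. SDA built from the work schedule.** Assumptions: 14 sets totalling 850 correct trials, growth 1.1 or 1.3 per set, beta-binomial number of completed sets, Beta consensus with mean 0.10, n = 50 or 100.
- Mean 5 sets: upper 2.8–3.9%, lower 0.7–2.0%
- Mean 7 sets: upper 2.7–3.5%, lower 1.3–2.2%
- Mean 10 sets: upper 2.2–2.7%, lower 2.1–2.6%

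A similar set-up at n = 100 with mean 5 sets and consensus mean 0.30 gave an upper tail of 2.60% and 2.80% for the two growth rates. The geometric schedule alone does not fix the skew; it also depends on how many sets people complete.

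**6. Empirical p-values on the same kind of data.** Using 1,999 shuffles and 2.5% per tail (upper / lower, %):

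| SDA; consensus | n | empirical | z rule |
|---|---|---|---|
| exponential; low | 100 | 2.44 / 2.29 | 3.39 / 1.33 |
| lognormal; low | 100 | 2.37 / 2.52 | 3.74 / 0.93 |
| exponential; low | 51 | 2.54 / 2.59 | 3.69 / 1.20 |
| lognormal; low | 51 | 2.48 / 2.62 | 4.12 / 0.73 |

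**7. What 10,000 shuffles can resolve.** The smallest two-sided p is 2 × 1/10,001 ≈ 0.0002. The robustness atlases have 84 and 360 regions, so 84 × 83/2 = 3,486 and 360 × 359/2 = 64,620 pairs. Edgewise Bonferroni would need 0.05/3,486 = 1.4 × 10⁻⁵ or 0.05/64,620 = 7.7 × 10⁻⁷, both out of reach.

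**The case against.** The plan claims a two-sided 5% level and nothing tail by tail, and every setting tried agrees with that claim to within a few tenths of a percentage point. Any imbalance depends on distributions that the documents do not report. The authors have also seen the problem: they plan an extent threshold on top of the edge cut, and they name a distribution-free alternative for this very reason.

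Most of this stands. A reader might infer that false edges are over-called in the direction H6a predicts. The documents do not support that. Total error is not raised, and the upper tail gains only if SDA and between-network consensus are skewed the same way. The cap of 14 sets makes a ceiling in SDA possible, and a left-skewed SDA with low consensus would push the error against H6a. A reader might also infer that the shuffles serve no purpose anywhere. That goes too far: if the extent threshold is calibrated on them, they do real work there.

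What does not stand is that these safeguards settle the matter. The text does not say that the extent threshold uses the shuffles, and PNF is only an option. The z cut is the one fully specified edge rule, and it decides which edges enter any component.

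**Conclusion.** The point holds for the edge-level step. As written, the rule is a fixed cut on |r|, the shuffles contribute nothing to it, and the shape of the null is discarded although the plan expects it to be non-standard. Neither the extent threshold nor the optional PNF changes this rule as the text stands.

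The size is modest. Two-sided error per edge stays near 5%. If both variables are right-skewed, the upper tail is about 2.7–4% and the lower about 1–2%, with 4.2% and 0.6% in the most extreme case tried at n = 51. With either variable symmetric there is no imbalance; with opposite skews it reverses.

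The reduction to a fixed cut needs only that the statistic is a simple correlation. The tail figures also assume Pearson r, exchangeable participants, no age adjustment and the illustrative distributions above. This is an inexpensive improvement that should be made before analysis; it does not show that H6a's overall error control fails.

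**What to change.** Replace the z-scoring sentence. For each association, compute an empirical p-value from the same 10,000 shuffles as twice the smaller tail proportion, with (count + 1)/10,001 in each tail, and use it in place of |z| > 1.96. Name the type of correlation.

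State that the extent threshold is calibrated on the same shuffles, through the maximum component size or a maximum statistic. This part is needed because empirical edge p-values do not themselves correct for the number of pairs, and 10,000 shuffles cannot support edgewise Bonferroni. Either commit to PNF or drop it. Apply the same rule to integration and centrality.

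Cost: SAP wording and slightly more analysis work. The shuffles are already planned and no new data are needed. A few edges may be gained or lost in each tail.

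### Hypothesis 6a calls edges significant at an uncorrected per-edge |z| > 1.96, and the added extent threshold is too loosely specified to show control of false positives

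*Combined protocol and SAP*

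**What the plan says.** All of this is in Statistical Considerations, Aim 3 Hypothesis Testing Plan, Hypothesis 6a, unless another place is named.

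- **Unit of test.** Region pairs: "The pairwise correlations between module consensus and SDA of participants represent a mapping of SDA into the functional connectome domain".
- **Use of the shuffles.** SDA is permuted, "where the SDA vectors will be randomly shuffled and their associations with modularity consensus mapped 10,000 times". The mean and standard deviation of that null turn each observed association into a z-score.
- **Significance rule.** The plan says "the actual SDA associations can be z-scored and thresholded at" p < 0.05, which it describes as "equivalent to a two tailed, i.e"., |z| > 1.96. It presents this as the rule for calling associations significant.
- **Second step.** To limit false positives further, "we will also incorporate the equivalent of an extent threshold for network-based associations". Extent may be counted as edges in connected components or as spatial clustering. No size is given, neither measure is chosen, and no reference distribution is named.
- **Alternative.** The Permutation Network Framework is something the team will consider. Under Power Analyses it is the alternative to permutation tests combined with an extent threshold.
- **Parcellation.** The primary analysis estimates connectivity "using a data-driven, functionally based parcellation and characterized for segregation/modularity", with no number of regions. The only counts given are for the robustness atlases, "from anatomically-based with 84 regions to multimodal with 360 regions, respectively".
- **Comparator.** Hypothesis 6b, the next analysis, commits to a false discovery rate below 0.05 with an extent threshold of k = 50.

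**The concern.** A threshold of |z| > 1.96 on each edge holds the error rate at 5% for one edge. It does not hold it for a map of thousands of edges. Ten thousand shuffles look like strong protection, but as described they only supply a mean and standard deviation for each edge, so they do not address multiplicity.

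The extent step therefore has to do all the work of separating signal from chance, and its rule is left open. If the cut-off is chosen after the map has been seen, or is simply a small number, the analysis could report a connected network related to SDA when no association exists. The same weakness would carry over to integration and centrality, which the plan evaluates in a similar way.

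**Working it through.** **Inputs.** From the plan: two-tailed 0.05 per edge, |z| > 1.96, 10,000 shuffles, atlases of 84 and 360 regions (Hypothesis 6a); n = 100 (Power Analyses); k = 50 (Hypothesis 6b). Assumed: the permutation z is about normal, and no edge is related to SDA (the global null).

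**1. The plan's own figure.** The two-sided 5% normal quantile is 1.95996, and |z| > 1.96 has two-sided probability 0.049996. The stated equivalence is correct for a single edge.

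**2. Expected false edges before the extent step.** With R regions there are m = R(R − 1)/2 edges, and the expected number of false edges is 0.05 × m. This expectation does not depend on how the edges are correlated, or on n.

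| R | m | 0.05 × m |
|---|---|---|
| 84 | 84 × 83/2 = 3,486 | 174.3 |
| 360 | 360 × 359/2 = 64,620 | 3,231 |

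If edges were independent, the chance of at least one false edge, 1 − 0.95^m, is 1 to any useful precision in both rows. For scale only, a two-sided Bonferroni rule would need |z| > 4.34 at 84 regions and |z| > 4.94 at 360.

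**3. Would a small component cut-off remove them?** At 5% density each region has on average (R − 1) × 0.05 false edges: 83 × 0.05 = 4.15 and 359 × 0.05 = 17.95. A random graph with mean degree well above 1 is dominated by one large component. Two null simulations measured this.

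*Independent edges, 300 replicates per atlas.*

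| R | Mean false edges | Share in largest component | Smallest largest-component |
|---|---|---|---|
| 84 | 175 | 99.97% | 143 edges |
| 360 | 3,234 | 100% | 3,078 edges |

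*Synthetic consensus matrices, n = 100, SDA generated independently of them.* The settings are assumptions: 7 modules, 40% of regions relabelled at random per participant, 10 partitions per participant with 20% further relabelling, and a skewed (gamma) SDA.

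| R | Replicates | Mean false edges | Mean largest component | Smallest largest-component |
|---|---|---|---|---|
| 84 | 150 | 166.2 | 166.0 | 123 edges |
| 360 | 15 | 3,130.9 | 3,130.9 | 2,916 edges |

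The observed rates in the second design, 166.2/3,486 = 4.8% and 3,130.9/64,620 = 4.8%, are close to the nominal 5%. A cut-off of 50 edges, borrowing the figure from Hypothesis 6b purely as an illustration (there it counts voxels), was passed in every null replicate of both designs. It removed almost none of the false edges.

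**The case against.** The strongest reply is that the plan does not rest on |z| > 1.96 alone. It commits to an extent step, and Power Analyses pairs permutation tests with an extent threshold or else uses the Permutation Network Framework. On that reading |z| > 1.96 only forms components and extent then filters them. Part of this stands: the counts above are pre-extent, and an extent rule drawn from the shuffles would control family-wise error. But Hypothesis 6a attaches the word significant to the edge threshold itself, and neither section says how the extent cut-off is set.

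Four stronger readings are tempting, and the documents do not support them.

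- **That the extent threshold is uncalibrated and will fail.** It is unspecified. Failure is shown only for a small arbitrary cut-off under assumed simulation settings.
- **That the primary analysis will yield 174 to 3,231 false edges.** Those figures belong to the robustness atlases; the primary parcellation may have another size.
- **That component size cannot separate signal from chance.** It can, once compared with the permutation distribution of the largest component. What is missing is that null.
- **That the plan's own remark about the test statistics, "they often show non-standard distributions due to the intrinsic complex nature of brain connectivity data", invalidates 1.96.** The remark is given as the reason for considering the alternative framework. No departure from normality has been shown, and the 5% count itself assumes approximate normality.

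The simulations use n = 100 as Power Analyses does, although Enrollment/Randomization sends only a subset to fMRI. The expected counts in step 2 are unaffected.

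**Conclusion.** The concern holds as a defect in the stated rule together with an incomplete second step. The edge-wise rule controls neither family-wise error nor the false discovery rate. Under the global null, with an approximately normal permutation z, 5% of edges are expected to be false before the extent step, which is about 174 at 84 regions and 3,231 at 360 as an illustrative bracket. The extent threshold might repair this, but the plan gives it no cut-off, no chosen measure and no permutation null, and the alternative framework is not a commitment. Error control is therefore not shown; the documents do not go so far as to establish that it is absent. Confidence is high on the uncorrected edge rule and on the arithmetic. It is lower on the behaviour of the extent step, which depends on a rule not yet written and on simulation settings that the documents do not supply.

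**What to change.** Amend Hypothesis 6a as follows.

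1. Name the primary parcellation and its number of regions in advance.
2. In each of the same 10,000 SDA shuffles, store one maximum: either (a) the largest |association| over all edges, or (b) the size of the largest component of edges passing |z| > 1.96. Choose (a) or (b) in advance; if (b), fix the extent measure too.
3. Declare significance only beyond the 95th percentile of that maximum distribution, which gives family-wise p < 0.05.
4. Keep |z| > 1.96 only as the component-forming threshold under (b), and remove it as a significance rule.

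Option (a) supports statements about single edges. Option (b) supports a statement about a component as a whole.

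The cost is SAP wording and one extra stored value per shuffle, with no new data or participants. The downside is that fewer edges will be declared significant.
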